### 10.5.2. Handling of Missing Data

Element	Reporting Detail
General	
 
Missing data occurs when any requested data is not provided, leading to blank fields on the collection instrument : 
 
These data will be indicated by the use of a “blank” in subject listing displays. Unless all data for a specific visit are missing in which case the data is excluded from the table.
 
Answers such as “Not applicable” and “Not evaluable” are not considered to be missing data and should be displayed as such.
 
 
 

Outliers	
 
Any subjects excluded from the summaries and/or statistical analyses will be documented along with the reason for exclusion in the clinical study report.
 

#### 10.5.2.1. Handling of Missing Dates

Element	Reporting Detail
General	Partial dates will be displayed as captured in subject listing displays.
Adverse Events	
 
The eCRF allows for the possibility of partial dates (i.e., only month and year) to be recorded for AE start and end dates; that is, the day of the month may be missing. In such a case, the following conventions will be applied for calculating the time to onset and the duration of the event: 
 
Missing Start Day: First of the month will be used unless this is before the start date of investigational product; in this case the study treatment start date will be used (and hence the event is considered On-treatment as per Appendix 3: Treatment States and Phases).
 
Missing Stop Day: Last day of the month will be used, unless this is after the stop date of study treatment; in this case the study treatment stop date will
 
 
 

Element	Reporting Detail
	
be used.
 
 
• Completely missing start or end dates will remain missing, with no imputation applied. Consequently, time to onset and duration of such events will be missing.
 
• Start or end dates which are completely missing (i.e. no year specified) will remain missing, with no imputation applied.
 

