9.1.1. Time Period and Frequency for Collecting AE and SAE Information

- All SAEs will be collected from the signing of the ICF until the follow-up visit at the time points specified in the SoA (Section 2).
- All AEs will be collected from the start of treatment until the follow-up visit at the time points specified in the SoA (Section 2).
- Medical occurrences that begin before the start of study treatment but after obtaining informed consent will be recorded on the Medical History/Current Medical Conditions section of the case report form (CRF) and not the AE section.
- All SAEs will be recorded and reported to the sponsor or designee immediately and under no circumstances should this exceed 24 hours, as indicated in [Appendix 5](#). The investigator will submit any updated SAE data to the sponsor within 24 hours of it being available.
- Investigators are not obligated to actively seek AEs or SAEs in former study participants. However, if the investigator learns of any SAE, including a death, at any time after a participant has been discharged from the study, and he/she considers the event to be reasonably related to the study treatment or study participation, the investigator must promptly notify the sponsor.
- The method of recording, evaluating, and assessing causality of AEs and SAEs and the procedures for completing and transmitting SAE reports are provided in [Appendix 5](#).

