#### 10.2.2.1. Treatment States for AE Data

Treatment State	Definition
Pre-Treatment	AE Start Date $<$ Study Treatment Start Date
On-Treatment	If AE onset date is on or after treatment start date & on or before the treatment stop date Study Treatment Start Date $\leq$ AE Start Date $\leq$ Study Treatment Stop Date [+ 1]
Post-Treatment	If AE onset date is after the treatment stop date AE Start Date $>$ Study Treatment Stop Date
Onset Time	If Treatment Start Date $>$ AE Onset Date = AE Onset Date - Treatment Start Date
Since First Dose (Days)	If Treatment Start Date $\leq$ AE Onset Date = AE Onset Date - Treatment Start Date + 1 Missing otherwise
Duration (Days)	AE Resolution Date – AE Onset Date + 1
Drug-related	If relationship is marked 'YES' on eCRF OR value is missing

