#### 10.5.2.2. Handling of Partial Dates

Element	Reporting Detail
Concomitant Medications	
 
• Partial dates for any concomitant medications recorded in the CRF will be imputed using the following convention: 
 
• If the partial date is a start date, a '01' will be used for the day and 'Jan' will be used for the month
 
• If the partial date is a stop date, a '28/29/30/31' will be used for the day (dependent on the month and year) and 'Dec' will be used for the month.
 
 
 
• The recorded partial date will be displayed in listings.
 

Adverse Events	
 
• Any partial dates for adverse events will be raised to data management. If the full date cannot be ascertained, the following assumptions will be made: 
 
• If the partial date is a start date, a '01' will be used for the day and 'Jan' will be used for the month.
 
• However, if these results in a date prior to Week 1 Day 1 and the event could possibly have occurred during treatment from the partial information, then the Week 1 Day 1 date will be assumed to be the start date.
 
• The AE will then be considered to start on-treatment (worst case).
 
• If the partial date is a stop date, a '28/29/30/31' will be used for the day (dependent on the month and year) and 'Dec' will be used for the month.
 
 
 
• The recorded partial date will be displayed in listings.
 

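### SAP 10.5.2.1 moves an AE with a missing start day to the dosing date even when its recorded month or end date proves it began earlier, giving a false On-Treatment state and sometimes an impossible duration

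*SAP*

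**What the plan says.** SAP 10.5.2.1 (Adverse Events) applies when month and year are recorded but "the day of the month may be missing". It sets conventions for computing time to onset and duration.

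- **Start day missing:** "First of the month will be used unless this is before the start date of investigational product". Where it is before that date, "in this case the study treatment start date will be used (and hence the event is considered On-treatment as per" the appendix on treatment states.
- **Stop day missing:** "Last day of the month will be used, unless this is after the stop date of study treatment", when the treatment stop date replaces it.

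SAP 10.2.2.1 defines a Pre-Treatment state for AEs that start before the treatment start date. It computes duration as "AE Resolution Date – AE Onset Date + 1", with no floor and no check that onset precedes resolution.

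SAP 10.5.2.2 gives a second rule for partial AE dates. They first go to data management. If the full date cannot be found, onset is moved to Day 1 only where "the event could possibly have occurred during treatment from the partial information". The SAP does not say which section governs.

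On what enters the data, protocol 9.1.1 states: "All SAEs will be collected from the signing of the ICF until the follow-up visit". Other AEs are collected only from the start of treatment. Screening, where consent is taken, runs up to 28 days before Day 1 (protocol Section 2).

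**The concern.** Moving an undated event to the dosing day is a reasonable worst-case convention when its timing is unknown. The only test in 10.5.2.1, however, is whether the first of the recorded month precedes dosing. That test is also met when the recorded month is wholly earlier than the dosing month, and when a known end date lies before dosing. In both situations the database already shows that the event came first, and the rule overrides it.

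The events exposed are SAEs, because they alone are collected before dosing. Such an SAE would be given a Day 1 onset and an On-Treatment state, although SAP 10.2.2.1 provides a Pre-Treatment state for it. If it had resolved before dosing, it would also get a duration that cannot exist.

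**Working it through.** The plan states no figure on this point, so the check applies its rules to cases. Calendar dates are illustrative. There is one dose, so treatment start and stop dates coincide.

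**Rules as written in 10.5.2.1.** Onset = dosing date if the first of the recorded month is before dosing. Duration = end - onset + 1.

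1. Start '-- May', end 20 May, dosed 10 June. Onset becomes 10 June, On-Treatment. Duration = -21 + 1 = **-20 days**. Month and end date both prove pre-dose onset.
2. Start '-- March', end '-- March', dosed 10 April. The end becomes 31 March, since the cap does not apply. Onset becomes 10 April. Duration = -10 + 1 = **-9 days**.
3. Start '-- April', end 10 April, dosed 20 April. Onset becomes 20 April. Duration = -10 + 1 = **-9 days**. Here only the end date gives the proof.
4. Start '-- March', end 12 April, dosed 10 April. Onset becomes 10 April. Duration = 2 + 1 = 3 days. This looks plausible, but the recorded month shows the onset and state are false.
5. Start '-- April', end 22 April, dosed 20 April. Onset becomes 20 April, duration 3 days. The timing really is ambiguous, and the convention works as intended.

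**General result.** Any pre-dose onset lies in a month whose first day is also before dosing, so every such event with a missing start day is moved. If it resolved before dosing, end is at most dosing - 1, so duration is at most 0. Take every onset 1 to 28 days before dosing with every later end date before dosing. That gives 1 + 2 + ... + 28 = 406 combinations per dosing date. Of these, 28 end the day before dosing (duration 0; 28/406 = 6.9%) and 378 are negative (93.1%).

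**How often the month alone is proof.** Assume onset is uniform over the W days before dosing and dosing days are spread evenly over a 365-day year. Dosing on day d of a month leaves W - d + 1 lags in the previous month (d up to W), which sum to W(W + 1)/2 per month. The share is 12 x [W(W + 1)/2] / (365W) = 6(W + 1)/365.

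- W = 7: 48/365 = 13%
- W = 14: 90/365 = 25%
- W = 28: 174/365 = 48%

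**Does 10.5.2.2 give the right answer in case 1?** Its guard keeps the event Pre-Treatment. Read literally, though, it also sets the start month to January: 1 January to 20 May is 31 + 28 + 31 + 30 + 20 = 140 days. Adopting it unchanged would correct the state but not the duration.

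**The case against.** The strongest reply is that the SAP already handles this. Section 10.5.2.2 covers the same dates, queries them first, and will not move an event that could not have occurred during treatment. That stands as mitigation, since a query will often recover the day. It is not a cure: no precedence is stated, and 10.5.2.1 could be the rule that is programmed.

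The trigger is also very narrow, and this stands in full. It needs an SAE after consent in someone still judged healthy and then dosed, with an onset day still unknown despite 24-hour SAE reporting and a query. Protocol 9.1.1 further sends medical occurrences between consent and dosing to Medical History rather than the AE section, without excepting serious ones. Whether pre-dose SAEs reach the AE data at all is therefore not fully clear.

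A reader might infer that one misplaced SAE would raise an arm's on-treatment rate from 0/6 to 1/6 in Table 2.3 and change the safety conclusion. The documents do not support that:

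- Table 2.3 has no on-treatment restriction in its title or programming notes, so a pre-dose SAE in a dosed participant might be counted whatever its state.
- Both 10.5.2.1 and 10.5.2.2 keep the partial date as recorded in listings, so Listing 15 would show '-- May' and a reader could see that the event came first.
- Drug-relatedness comes from the eCRF answer (or its absence), not from the imputed onset.
- No statistical analysis of safety is planned (SAP 8.1.1.1), and no decision rule depends on SAE counts.

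**Conclusion.** The start-day rule in SAP 10.5.2.1 is wrong as written. It overrides recorded information that proves pre-dose onset, and it conflicts with 10.5.2.2 without a stated order of precedence. The effect is confined to derived onset, duration and treatment state. Every pre-dose SAE with a missing start day handled by this rule becomes On-Treatment, and every one that resolved before dosing gets a duration of zero or less.

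The 13% to 48% range rests on uniform onset and on the assumed length of the pre-dose window. The upper end needs the full 28 days. It describes only such SAEs, and with about 12 participants there may well be none. This is a desirable clarification and no threat to the trial's conclusions.

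**What to change.** Reconcile 10.5.2.1 and 10.5.2.2 into one rule for partial AE dates:

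- Query the date with data management first.
- If the start day stays unknown, use the treatment start date only when the recorded month and year are those of dosing and any known end date is on or after dosing.
- If the recorded month is earlier than the dosing month, or the event ended before dosing, use the later of the first of the recorded month and the consent date, and class the event as Pre-Treatment.
- Keep the first of the month where the recorded month begins after dosing.

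The consent bound matters because SAEs are collected only from consent. With consent on 25 May, start '-- May', end 30 May and dosing on 10 June, the first of the month alone would give 30 days and an onset before consent. The bounded rule gives 30 - 25 + 1 = 6 days. In case 1, with consent on 13 May (28 days before dosing), it gives 20 - 13 + 1 = 8 days, Pre-Treatment. The ambiguous case 5 is still moved to the dosing date.

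At the same time, correct the cross-reference in 10.5.2.1, which points to Appendix 3 for treatment states; they are in Appendix 2. The cost is a few sentences in the SAP and one condition in the derivation program, with no effect on conduct or participants.

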#### 10.5.2.2. Handling of Partial Dates

Element	Reporting Detail
Concomitant Medications	
 
• Partial dates for any concomitant medications recorded in the CRF will be imputed using the following convention: 
 
• If the partial date is a start date, a '01' will be used for the day and 'Jan' will be used for the month
 
• If the partial date is a stop date, a '28/29/30/31' will be used for the day (dependent on the month and year) and 'Dec' will be used for the month.
 
 
 
• The recorded partial date will be displayed in listings.
 

Adverse Events	
 
• Any partial dates for adverse events will be raised to data management. If the full date cannot be ascertained, the following assumptions will be made: 
 
• If the partial date is a start date, a '01' will be used for the day and 'Jan' will be used for the month.
 
• However, if these results in a date prior to Week 1 Day 1 and the event could possibly have occurred during treatment from the partial information, then the Week 1 Day 1 date will be assumed to be the start date.
 
• The AE will then be considered to start on-treatment (worst case).
 
• If the partial date is a stop date, a '28/29/30/31' will be used for the day (dependent on the month and year) and 'Dec' will be used for the month.
 
 
 
• The recorded partial date will be displayed in listings.
 

## 10.6. Appendix 6: Values of Potential Clinical Importance

### 10.6.1. Laboratory Values

Haematology				
Laboratory Parameter	Units	Category	Clinical Concern Range	
			Low Flag (< x)	High Flag (>x)
Hematocrit	Ratio of 1	Male		0.54
		Female		0.54
		Δ from BL	↓0.075	
Hemoglobin	g/L	Male		180
		Female		180
		Δ from BL	↓25	
Lymphocytes	x10  / L		0.8	
Neutrophil Count	x10  / L		1.5	
Platelet Count	x10  / L		100	550
White Blood Cell Count (WBC)	x10  / L		3	20

Clinical Chemistry				
Laboratory Parameter	Units	Category	Clinical Concern Range	
			Low Flag (< x)	High Flag (>x)
Calcium	mmol/L		2	2.75
Creatinine	mmol/L	Δ from BL		↑ 44.2
Glucose	mmol/L		3	9
Potassium	mmol/L		3	5.5
Sodium	mmol/L		130	150

Liver Function				
Test Analyte	Units	Category	Clinical Concern Range	
ALT/SGPT	U/L	High	≥ 2x ULN	
AST/SGOT	U/L	High	≥ 2x ULN	
AlkPhos	U/L	High	≥ 2x ULN	
T Bilirubin	µmol/L	High	≥ 1.5xULN	
T. Bilirubin + ALT	µmol/L U/L	High	1.5xULN T. Bilirubin + ≥ 2x ULN ALT	

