12.6. Appendix 6: Clinical Laboratory Tests

- The tests detailed in [Table 3](#) will be performed by the local laboratory.
- Protocol-specific requirements for inclusion or exclusion of participants are detailed in Section [6](#) of the protocol.
- Additional tests may be performed at any time during the study as determined necessary by the investigator or required by local regulations.

Table 3 Protocol-Required Safety Laboratory Assessments

Laboratory Assessments	Parameters			
Hematology	Platelet Count	RBC Indices: Mean corpuscular volume (MCV) Mean corpuscular hemoglobin (MCH) %Reticulocytes	White blood cell (WBC) count with Differential: Neutrophils Lymphocytes Monocytes Eosinophils Basophils	
	Red blood cell (RBC) Count			
	Hemoglobin			
	Hematocrit			
Clinical Chemistry ¹	Blood urea nitrogen (BUN)	Potassium	Aspartate Aminotransferase (AST)/ Serum Glutamic-Oxaloacetic Transaminase (SGOT)	Total and direct bilirubin
	Creatinine	Sodium	Alanine Aminotransferase (ALT)/ Serum Glutamic-Pyruvic Transaminase (SGPT)	Total Protein
	Glucose (fasting for screening)	Calcium	Alkaline phosphatase	
Routine Urinalysis	
 • Specific gravity • pH, glucose, protein, blood, ketones, bilirubin, urobilinogen, nitrite, leukocyte esterase by dipstick • Microscopic examination (if blood or protein is abnormal) 			
Other Screening Tests	
 • Follicle-stimulating hormone and estradiol (as needed in women of non-childbearing potential only) • Urine alcohol and drug screen (to include at minimum: amphetamines, barbiturates, cocaine, opiates, cannabinoids and benzodiazepines) • Serum or urine human chorionic gonadotropin (hCG) pregnancy test (as 			

Laboratory Assessments	Parameters
	
needed for women of childbearing potential)²
 
 • Serology [(HIV antibody, hepatitis B surface antigen [HBsAg], and hepatitis C virus antibody)] • additional local laboratory assessments are needed, include the following: and list the exceptions. The results of each test must be entered into the CRF.

NOTES :

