#### 10.8.4. Safety Tables

Safety Tables					
No.	Population	IDSL / TST ID / Example Shell	Title	Programming Notes	Deliverable [Priority]
Adverse Events					
2.1	Safety	CP_AE1p	Summary of All Adverse Events		SAC [1]
2.2	Safety	CP_AE1p	Summary of All Drug-Related Adverse Events	Include total column.	SAC [1]
2.3	Safety	CP_AE1p	Summary of Serious Adverse Events		SAC [1]
2.4	Safety	AE15	Summary of Common (>=5%) Non-serious Adverse Events by System Organ Class and Preferred Term (Number of Subjects and Occurrences)		SAC [1]
2.5	Safety	CP_AE1p	Summary of Adverse Events Leading to Permanent Discontinuation of Study Drug or Withdrawal from Study		SAC [1]
Labs					
2.6	Safety	LB1	Summary of Chemistry Changes from Baseline		SAC [1]
2.7	Safety	LB17	Summary of Emergent Chemistry Results by Potential Clinical Importance (PCI) Criteria		SAC [1]
2.8	Safety	LB1	Summary of Haematology Changes from Baseline		SAC [1]
2.9	Safety	LB17	Summary of Emergent Haematology Results by Potential Clinical Importance (PCI) Criteria		SAC [1]

Safety Tables					
No.	Population	IDSL / TST ID / Example Shell	Title	Programming Notes	Deliverable [Priority]
2.10	Safety	UR3b (LB1)	Summary of Urinalysis Results by Planned Timepoint	Use shell UR3b for: pH, glucose, protein, blood, ketones, bilirubin, urobilinogen, nitrite, leukocyte esterase as these are collected by dipstick  Use shell LB1 for: Specific gravity	SAC [1]
ECGs					
2.11	Safety	EG1	Summary of ECG Findings		SAC [1]
2.12	Safety	EG2	Summary of ECG Values		SAC [1]
2.13	Safety	EG2	Summary of Change from Baseline in ECG Values		SAC [1]
Vital Signs					
2.14	Safety	VS1	Summary of Change from Baseline in Vital Signs		SAC [1]
2.15	Safety	VS7	Summary of Emergent Vital Signs Results by Potential Clinical Importance (PCI) Criteria		SAC [1]
Spirometry					
2.16	Safety		Summary of Spirometry (FVC and FEV1)	See example: uk1salx00175/gsk2269557/mid205759/final/Table 2.35	SAC [1]
2.17	Safety		Summary of Change from Baseline in Spirometry (FVC and FEV1)	See example: uk1salx00175/gsk2269557/mid205759/final/Table 2.38	SAC [1]

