### 10.8.7. ICH Listings

ICH Listings					
No.	Population	IDSL / TST ID / Example Shell	Title	Programming Notes	Deliverable [Priority]
Randomisation					
1	Safety	CP_TA1	Listing of Randomised and Actual Treatments		SAC [1]
Subject Disposition					
2	Safety	ES2	Listing of Reasons for Study Withdrawal		SAC [1]
3	APE	ES7	Listing of Reasons for Screening Failure		SAC [1]
4	Safety	BL1	Listing of Subjects for Whom the Treatment Blind was Broken		SAC [1]
5	Safety	SP3	Listing of Subjects Excluded from PK Population		SAC [1]
6	Safety	DV2	Listing of Important Protocol Deviations		SAC [1]
7	Safety	IE3	Listing of Subjects with Inclusion/Exclusion Criteria Deviations		SAC [1]
Demographics					
8	Safety	DM2	Listing of Demographic Characteristics		SAC [1]
9	Safety	DM9	Listing of Race		SAC [1]
Prior and Concomitant Medications					
10	Safety	CP_CM3	Listing of Concomitant Medications		SAC [1]
11	Safety	MH2	Listing of Current and/or Past Medical Conditions		

ICH Listings					
No.	Population	IDSL / TST ID / Example Shell	Title	Programming Notes	Deliverable [Priority]
Exposure and Treatment Compliance					
12	Safety	EX3	Listing of Exposure Data		SAC [1]
Adverse Events					
13	Safety	AE7	Listings of Subject Numbers for Individual Adverse Events		SAC [1]
14	Safety	AE8	Listing of All Adverse Events		SAC [1]
15	Safety	AE8	Listing of Serious Adverse Events		SAC [1]
16	Safety	AE8	Listing of Adverse Events Leading to Withdrawal from Study / Permanent Discontinuation of Study Treatment		SAC [1]
LABS					
17	Safety	CP_LB5	Listing of All Clinical Chemistry Laboratory Data for Subjects with PCI Abnormalities		SAC [1]
18	Safety	CP_LB5	Listing of All Haematology Laboratory Data for Subjects with PCI Abnormalities		SAC [1]
19	Safety	CP_LB5	Listing of Clinical Chemistry Abnormalities of Potential Clinical Importance		
20	Safety	CP_LB5	Listing of Haematology Abnormalities of Potential Clinical Importance		
ECGs					

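### The SAP's only creatinine flag is a rise above 44.2 mmol/L; number and unit do not fit, and in that unit it cannot flag anything

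*SAP*

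**What the plan says.** The Clinical Chemistry table in SAP Section 10.6.1 has one row for creatinine: "Creatinine mmol/L Δ from BL ↑ 44.2". The value stands in the high-flag column, which is strict (greater than x). The row gives no absolute limit, and neither document has another creatinine criterion.

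All five rows of that table (calcium, creatinine, glucose, potassium, sodium) carry mmol/L. The Liver Function table in the same section uses the micro unit: "T Bilirubin µmol/L".

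The criteria feed three planned displays:

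- Table 2.7: "Summary of Emergent Chemistry Results by Potential Clinical Importance (PCI) Criteria"
- Listing 17: "Listing of All Clinical Chemistry Laboratory Data for Subjects with PCI Abnormalities"
- Listing 19: "Listing of Clinical Chemistry Abnormalities of Potential Clinical Importance"

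Table 2.6, "Summary of Chemistry Changes from Baseline", does not use them.

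Protocol Appendix 6 (Section 12.6) says that the tests "will be performed by the local laboratory". Its Table 3 lists creatinine without a unit, so the documents do not say in which unit the values will arrive.

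**The concern.** A creatinine change of 44.2 mmol/L is far outside anything a blood sample could show, whereas 44.2 µmol/L is a change of a size one might want to flag. The likeliest explanation is that mmol/L was carried down the column from the electrolyte and glucose rows.

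A programmer who follows the SAP faithfully, converting the data to the printed unit and comparing with 44.2, would switch the flag off. Table 2.7 and Listing 19 would then contain no creatinine flag whatever the data were, and a reader could take that absence as reassurance. The SAP plans no chemistry listing for all participants: both chemistry listings depend on PCI status. A participant whose only abnormality was a creatinine rise would therefore appear in no planned participant-level laboratory listing. Laboratory safety data are a named component of the secondary endpoint, and the schedule of activities has a single post-dose draw, on Day 2.

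**Working it through.** The documents give no derivation of 44.2, so there is no stated calculation to reproduce. The check is a unit conversion followed by a test of what the rule would flag.

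**Inputs**

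- From SAP Section 10.6.1: rise from baseline, strict inequality, 44.2, mmol/L.
- From SAP Section 10.3.2.1: baseline is the last assessment before dosing.
- Assumed, not in the documents: creatinine (C4H7N3O) molar mass = 4 × 12.011 + 7 × 1.008 + 3 × 14.007 + 15.999 = 113.12 g/mol; range tried 113.0 to 113.2.
- Assumed, not in the documents: baseline creatinine between 40 and 150 µmol/L (0.04 to 0.15 mmol/L).

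**Conversion**

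- Printed unit: 44.2 mmol/L × 113.12 mg/mmol = 4999.9 mg/L, or 500.0 mg/dL (499.5 to 500.3 over the range of molar mass).
- Same number in µmol/L: 44.2 µmol/L = 0.0442 mmol/L; 0.0442 × 113.12 = 5.0 mg/L, or 0.50 mg/dL.
- Ratio: 44.2 / 0.0442 = 1000.

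**What the rule flags**

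The fold increase needed for a flag is (baseline + limit) / baseline.

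| Baseline (µmol/L) | Fold needed, limit 44.2 mmol/L | Fold needed, limit 44.2 µmol/L |
|---|---|---|
| 40 | 44.24 / 0.04 = 1106 | 84.2 / 40 = 2.1 |
| 80 | 44.28 / 0.08 = 554 | 124.2 / 80 = 1.55 |
| 150 | 44.35 / 0.15 = 296 | 194.2 / 150 = 1.29 |

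Even a rise from 80 to 3000 µmol/L is only 2.92 mmol/L and is not flagged in the printed unit. Within the SAP's own table, 44.2 mmol/L is 4.9 times the high glucose flag (44.2 / 9).

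**What Table 2.6 would still show**

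As an illustration only, suppose one of six participants in an arm goes from 80 to 125 µmol/L and the other five do not change. The rise of 45 µmol/L exceeds 44.2 µmol/L, so it would be flagged in that unit; it is 0.045 mmol/L and would not be flagged in the printed unit. The arm's change from baseline has mean 45 / 6 = 7.5, sample SD 45 / √6 = 18.4, median 0 and maximum 45 µmol/L. A summary with an SD or maximum would reveal the rise without identifying the participant; a mean alone would show it weakly. Which statistics are printed depends on IDSL Statistical Principle 6.06.1, cited in SAP Section 10.3.3 but not reproduced.

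**The case against.** Four points can be made in the plan's defence.

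*The text may have been misread.* A micro sign taken for the letter m when the PDF was converted would give exactly this row, and the micro sign is not read uniformly elsewhere (Protocol Section 3.2 shows two forms). Against that, both bilirubin rows in the same SAP section keep µmol/L, and the Δ and ↑ symbols survive in the creatinine row itself. A reading fault is unlikely but not excluded. What stands is that confidence is high for the printed text and somewhat lower for an error in the sponsor's own file.

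*The output may be right anyway.* If the data are held in µmol/L and compared with 44.2, the flag works. That is true, and the effect may be nil in practice. But it depends on the programmer disregarding the printed unit, and the documents do not state the laboratory's unit.

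*The case rests on outside facts.* Molar mass and the usual creatinine range are not in the documents. They are declared above with ranges, and no reasonable choice closes a gap of 1000.

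*Little depends on it.* This stands, and it sets the weight. The study has about 12 participants, one dose and one scheduled post-dose draw. Table 2.6 covers creatinine change. Protocol Section 9.3.5 requires the investigator to review each laboratory report, record clinically relevant changes as adverse events and file the report as source. Analysis datasets will hold the individual values. A participant flagged on another chemistry analyte would have creatinine shown in Listing 17.

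**Conclusion.** The concern holds, as a minor error. The only creatinine criterion is wrong as printed by a factor of 1000 relative to the same number in µmol/L, on the assumptions of a molar mass near 113.12 g/mol and baseline values of 40 to 150 µmol/L. Followed literally, it could not flag any creatinine rise. That µmol/L was intended is an inference; neither document states the intended limit. The documents also give no basis for the probability of a rise large enough to matter. The consequence is confined to creatinine in Table 2.7 and Listings 17 and 19; the primary pharmacokinetic analysis and the sample size reasoning do not use this limit.

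**What to change.** 1. Check the creatinine row in the source PDF of the SAP.
2. Reconcile number and unit with the sponsor's source PCI criterion. If that criterion is 44.2 µmol/L, print µmol/L with ↑44.2 or, equivalently, mmol/L with ↑0.0442. If it is something else, print that.
3. Confirm the local laboratory's creatinine reporting unit, and the unit in the analysis dataset, before programming Table 2.7 and Listings 17 and 19.

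The cost is one cell in the SAP and two short checks. No data collection, schedule or analysis method changes.
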